### **c) Delayed Onset Muscle Soreness (DOMS):**

The perception of Delayed Onset Muscle Soreness (DOMS) was assessed using the Numeric Rating Scale (NRS). The scale was numbered from 0 to 10, where 0 indicated the absence of muscle pain, and 10 indicated maximum muscle pain during a maximum voluntary contraction for knee extension in a seated position. The choice of NRS was based on its reliability and responsiveness, as reported by .

[figure not shown]
The location and extent (percentage area) of DOMS were assessed using a pain map (mapDOMS) using a body chart representing the human body from different views (frontal, lateral, and dorsal). Two variables, the extent and location of pain, were used following the approach proposed by . Briefly, the areas where athletes reported pain were marked and later measured in cm. The painted area was then calculated using ImageJ software, an open-source software created by Wayne Rasband at the National Institutes of Health (NIH) in 1987 . Finally, the painted area was calculated as a percentage (%) of the total area related to the lower limbs.

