### STATISTICAL ANALYSIS PLAN (SUMMARY)

Primary endpoint: Serum CK levels (U/L) over time.

Secondary endpoints: DOMS (NRS and mapDOMS), SJ and CMJ jump heights (cm), and isometric knee extensor force (kgf).

Statistical tests:

- Normality (Shapiro–Wilk) and homogeneity (Levene).
- Two-way repeated measures ANOVA with Tukey post hoc (parametric).
- Friedman and Kruskal–Wallis (nonparametric when assumptions not met).
- Significance level:  $\alpha = 0.05$ .

Software: IBM SPSS Statistics v20.0.

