## Data Analysis

Data analysis was conducted by a researcher blinded to participant group allocation. The primary outcome of the study was considered the muscle damage measured by CK levels.

The data were descriptively analyzed using mean and standard deviation. The independent variables were the experimental conditions (Sham, PBM-pre, and PBM-post) and assessment times pre, 24h, 48h, 72h after the muscle damage induction protocol. Normality and homoscedasticity assumptions were tested beforehand using the Shapiro-Wilk W Test and Levene test, respectively. The dependent variables included CK, DOMS, height of jumps in Squat Jump (SJ) and Counter Movement Jump (CMJ), and isometric manual dynamometry of the femoral quadriceps (kgf).

Two-way repeated measures analysis of variance (ANOVA) was conducted (considering pre, 24h, 48h, and 72h after the muscle damage induction protocol) followed by Tukey's post hoc test when the data showed normal distribution and variance homogeneity. In cases where the data did not present normal distribution, a logarithmic transformation (log10) was adopted, and normality and variance homogeneity were verified again for parametric tests. If the data did not meet the assumptions of normality and variance homogeneity, non-parametric tests such as Friedman's ANOVA (intragroup analyses) and Kruskal-Wallis (intergroup analyses) were employed. The significance level was set at 5%. Statistical analysis was performed using a statistical software (SPSS Statistics for Windows version 20.0, IBM, Chicago, IL, United States).

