## RESULTS

Thirty male professional football players (high level) from the same team were recruited and completed all procedures of this study. Therefore, there were no dropouts, and intention-to-treat analysis was not necessary. Anthropometric data are described in Table 4. No adverse effects were reported during the study.

**Table 4.** Anthropometric data of the investigated athlete sample. Values in mean ( $\pm$  standard deviation):

| Groups | Age (years)  | Body Mass (kg) | BMI
(kg/m^2) | Years of Practice | Fitzpatrick
Phototype          |
|---------------|---------------------|-----------------------|-----------------------------------|--------------------------|-------------------------------------------|
| Sham   | 18.70 ( $\pm$ 0.82) | 76.03 ( $\pm$ 13.27)  | 22.62 ( $\pm$ 2.10)               | 9.60 ( $\pm$ 1.77)       | Type I: 2,
Type II: 0,
Type III: 3, |

|                 |                      |                      |                      |                      |                                                                       |
|-----------------|----------------------|----------------------|----------------------|----------------------|-----------------------------------------------------------------------|
|                 |                      |                      |                      |                      | Type IV: 3,
Type V: 2                                              |
| PBM-pre  | 20.50 ( $\pm 4.30$ ) | 70.43 ( $\pm 4.90$ ) | 23.07 ( $\pm 0.94$ ) | 11.30 ( $\pm 3.74$ ) | Type I: 2,
Type II: 2,
Type III: 3,
Type IV: 2,
Type V: 1 |
| PBM-post | 21.22 ( $\pm 7.44$ ) | 76.13 ( $\pm 8.03$ ) | 23.48 ( $\pm 1.73$ ) | 11.44 ( $\pm 3.46$ ) | Type I: 3,
Type II: 5,
Type III: 1,
Type IV: 1,
Type V: 0 |

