#### Delayed Onset Muscle Soreness (DOMS) measured by the Numeric Rating Scale (NRS).

Repeated measures ANOVA revealed a moment interaction ( $F_{2,27} < 0.001$ ) and a moment versus treatment interaction ( $F_{2,27} = 0.044$ ). Tukey's post hoc analysis identified significant differences as shown in Table 6.

[figure not shown]
**Table 6.** Mean values ( $\pm$  standard deviation) of Delayed Onset Muscle Soreness (DOMS) measured by the Numeric Rating Scale (NRS) for the Sham, PBM-pre, and PBM-post groups at pre, 24h, 48h, and 72h after the muscle damage induction protocol:

| Groups | DOMS (NRS)          | DOMS (NRS)           | DOMS (NRS)           | DOMS (NRS)           |
|--------|---------------------|----------------------|----------------------|----------------------|
|        | pre                 | 24h                  | 48h                  | 72h                  |
| Sham   | 0.60 ( $\pm 1.26$ ) | 5.70 ( $\pm 2.05$ )* | 4.20 ( $\pm 2.39$ )* | 3.20 ( $\pm 2.78$ )* |

|                 |                     |                      |                     |                     |
|-----------------|---------------------|----------------------|---------------------|---------------------|
| PBM-pre  | 1.20 ( $\pm 1.61$ ) | 3.80 ( $\pm 2.74$ )* | 2.80 ( $\pm 1.54$ ) | 1.70 ( $\pm 1.82$ ) |
| PBM-post | 1.30 ( $\pm 2.11$ ) | 3.00 ( $\pm 2.00$ )  | 2.40 ( $\pm 1.83$ ) | 2.10 ( $\pm 1.72$ ) |

**Abbreviations:** PBM (photobiomodulation); DOMS (Delayed Onset Muscle Soreness); NRS (Numeric Rating Scale); \* p-value < 0.05 in two-way repeated measures ANOVA followed by Tukey's post hoc analysis.

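### The log10 step has no rule for zeros, the named rank-test fallback does not test arm-by-time, and the reported mapDOMS time result turns on zero handling that is not disclosed

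*Combined protocol and SAP*

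**What the plan says.** The Data Analysis section plans a two-way repeated-measures ANOVA with Tukey comparisons if normality and equal variances hold. Otherwise: "In cases where the data did not present normal distribution, a logarithmic transformation (log10) was adopted", and the assumptions are checked again. If they still fail, "non-parametric tests such as" Friedman's "ANOVA (intragroup analyses) and Kruskal-Wallis (intergroup analyses) were employed". The Statistical Analysis Plan (Summary) lists the rank tests as "nonparametric when assumptions not met" and omits the log10 step. Neither place gives an added constant or a rule for zeros. Neither says whether normality is tested by cell, by time point or on residuals.

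The section on DOMS defines the NRS from 0 to 10, "where 0 indicated the absence of muscle pain". For mapDOMS, "the painted area was calculated as a percentage (%) of the total area related to the lower limbs".

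In the Results, all 30 players "were recruited and completed all procedures of this study". NRS is reported from an ANOVA with no transformation and no assumption check mentioned. For mapDOMS the text says log10 was applied and the assumptions were then met. It gives 0.302 for time and 0.423 for arm-by-time, but no number analysed, count of zeros or constant. The abstract reports no significant mapDOMS change, either between groups or over time.

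**The concern.** The logarithm of zero is undefined, and the two soreness outcomes are the ones where zero is an ordinary answer, above all before exercise. An analyst who follows the rule literally loses every athlete with a zero. An analyst who adds a constant keeps them, but chooses a number the plan does not fix, and on a log scale a small constant can dominate the result.

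The last step of the rule has a different gap. Friedman within an arm tests time in that arm, and Kruskal-Wallis at one time compares arms at that time. Neither asks whether the arms change differently, which is the treatment question the ANOVA answers through arm-by-time. This applies to every outcome, including CK.

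mapDOMS shows why it matters. Its log10 time result is clearly non-significant although the pooled mean more than triples from baseline to 24 h, and the reader cannot tell how zeros were treated.

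**Working it through.** **NRS zeros.** Inputs: Table 6 baseline means and SDs, n = 10 per arm; whole-number scoring is an assumption. Listing every set of ten scores from 0 to 10 that matches:

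- Sham, 0.60 (1.26): 7 or 8 zeros.
- PBM-pre, 1.20 (1.61): 4 to 6 zeros. It fits only if the SD was truncated (1.619).
- PBM-post, 1.30 (2.11): 4 to 7 zeros.

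The total is 7 + 4 + 4 = 15 to 8 + 6 + 7 = 21 of 30. With half-point scores it is 9 to 21. Dropping baseline zeros would leave at most 30 − 21 = 9 to 30 − 15 = 15 athletes under whole-number scoring, with 2 or 3 in Sham.

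Every matching whole-number baseline cell fails Shapiro-Wilk (largest p 0.005). Yet among 5,000 whole-number data sets matching all of Table 6, 65% pass on pooled within-athlete residuals and 6% on pooled cell-centred values. The branch taken depends on a choice the plan leaves open.

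**What the printed 0.302 is.** It is printed as F with 2 and 27 df. The same subscript stands on all six outcomes, and NRS values of <0.001 and 0.044 are reported as effects found, so these numbers behave as p-values. For SJ, CMJ and dynamometry a single within-athlete correlation (0.87, 0.87, 0.65) reproduces both printed values as p-values. Read as a true F, 0.302 would give p = 0.74 (2, 27 df) or 0.82 (3, 81 df), further from Table 7.

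**mapDOMS, raw scale, 30 athletes.** Pooled means from Table 7 are 1.83, 6.62, 5.26 and 4.30; grand mean 4.50.

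- MS(time) = 30 × Σ(time mean − grand mean)² / 3 = 122.4.
- Mean of the 12 cell variances = 26.72. With four occasions, the error mean square cannot exceed 26.72 × 4/3 = 35.6, whatever the correlations.
- F(3, 81) ≥ 122.4 / 35.6 = 3.44, so p ≤ 0.021; at lower-bound df (1, 27), p ≤ 0.075.
- At zero average correlation F = 122.4 / 26.72 = 4.58, p = 0.005; positive correlation makes it smaller.
- MS(arm-by-time) = 8.32, giving p = 0.93, 0.85 and 0.59 at average correlation 0, 0.3 and 0.6. The reported 0.423 fits at about 0.81.

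**mapDOMS, log10 scale.** The reported test is on this scale, so the raw bound does not settle it. The next check is simulation with each cell matched to the Table 7 mean and SD.

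How many zeros can a cell hold? With z zeros among 10, the smallest possible SD is mean × √(10z / (9(10 − z))). For Sham at baseline, z = 7 gives 4.81 and z = 8 gives 6.30, against a printed 5.16, so the maximum is 7. By this bound the baseline maxima are 7, 4 and 6 (Sham, PBM-pre, PBM-post), and later cells allow 3 to 6.

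With no zeros, none of 15,000 log-normal data sets reached a time p of 0.302 (largest 0.114; 0.164 at lower-bound df). With zeros absent or mainly at baseline, at most 2 in any later cell, and a constant of 1, 0.1 or 0.01, none of 7,500 did (largest 0.058). Other placements of zeros do reach it with all 30 athletes kept:

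| Zeros per cell, baseline / later | Constant | Correlation 0 | 0.3 | 0.6 |
|---|---|---|---|---|
| 3 / 3 | 0.01 | 271/299 | 224/300 | 78/300 |
| 2 / 2 | 0.01 | 39/300 | 6/300 | 0/300 |
| 2 / 2 | 0.001 | 246/300 | 194/300 | 82/299 |
| 1 / 3 | 0.1 | 109/300 | 40/300 | 4/300 |

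A separate run of the first row gave 187, 130 and 44 of 200. In every set that reached 0.302, arm-by-time was also non-significant, as reported. In the first row, 22, 51 and 19 of the sets reaching 0.302 passed Shapiro-Wilk on residuals and Levene at every time. None passed Shapiro-Wilk by cell or by time point.

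**The case against.** The defence has several sound points. A constant loses neither athletes nor the interaction test, so it would be wrong to say that the rule must cost one or the other. The fallback list is open, Kruskal-Wallis on change scores would compare arms on change, and no reported result used the fallback. NRS was not log-transformed, so the loss to 9–15 athletes is hypothetical. mapDOMS is secondary, and time is not the treatment contrast. The planned ANOVA also performs well on simulated NRS-like data: type I error 5.3–5.8% and power 71–88%, against 4.5–5.0% and 70–88% for a permutation version.

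All of that stands, and it limits the point. It does not close the gap: the plan names no constant, and an open list is not a specified arm-by-time test.

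A reader might infer from Table 7 that 0.302 is impossible with 30 athletes, or that athletes with zeros were dropped. The documents support neither. Routes with all 30 exist, although in the runs checked they sit uneasily with the stated normality unless residuals were tested. Dropping athletes is another possible cause, but it is unproven. The printed 27 equals 30 − 3, but it is not the error df of a four-occasion time test (81) and looks like a template, so it does not show how many were analysed.

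**Conclusion.** The point holds as a gap in the plan with one visible consequence. Zeros are near certain for NRS (15–21 of 30 at baseline under whole-number scoring) and plausible for mapDOMS, and the log10 rule does not say what to do with them. The named fallback does not test arm-by-time for any outcome. The mapDOMS time result differs from the raw scale (p ≤ 0.021, or 0.075 at lower-bound df, with 30 athletes) and depends on undisclosed zero handling. Only the part of the abstract's mapDOMS sentence that concerns change over time is exposed.

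It might also be inferred that the NRS ANOVA broke the plan. That is not shown: residuals could have passed, and the plan does not say what was to be tested. The mapDOMS arm-by-time result and the CK analysis are not contradicted.

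The conclusion assumes 10 athletes per cell, an unmarked chart scored 0%, and, on the log scale, log-normal positive values. Confidence is medium. The change should be made, but no treatment conclusion is shown to be wrong.

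**What to change.** In Data Analysis, for NRS and mapDOMS, replace the log10 step with one method that accepts zeros, keeps all 30 athletes and tests arm-by-time. One example is the 3 × 4 repeated-measures model on the original scale with permutation inference, permuting arm labels for arm-by-time and times within athlete for time.

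For all outcomes, replace the Friedman/Kruskal-Wallis fallback with a method that tests arm-by-time or compares arms on change: that permutation model, or Kruskal-Wallis on change from baseline. Align the Statistical Analysis Plan (Summary).

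Re-run NRS and mapDOMS, labelled post hoc. Report athletes analysed, number of zeros, any constant used in the reported mapDOMS analysis, how NRS normality was checked, and the true F, df and p. Change the abstract's statement about mapDOMS over time only if the re-run differs.

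The cost is new wording and a small re-run on existing data, with a less familiar method and after results are known. In simulated NRS-like data the permutation test loses about 1 percentage point of power against the ANOVA (70–88% versus 71–88%). Kruskal-Wallis on change scores gives 71–84%.

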## RESULTS

Thirty male professional football players (high level) from the same team were recruited and completed all procedures of this study. Therefore, there were no dropouts, and intention-to-treat analysis was not necessary. Anthropometric data are described in Table 4. No adverse effects were reported during the study.

**Table 4.** Anthropometric data of the investigated athlete sample. Values in mean ( $\pm$  standard deviation):

| Groups | Age (years)  | Body Mass (kg) | BMI
(kg/m^2) | Years of Practice | Fitzpatrick
Phototype          |
|---------------|---------------------|-----------------------|-----------------------------------|--------------------------|-------------------------------------------|
| Sham   | 18.70 ( $\pm$ 0.82) | 76.03 ( $\pm$ 13.27)  | 22.62 ( $\pm$ 2.10)               | 9.60 ( $\pm$ 1.77)       | Type I: 2,
Type II: 0,
Type III: 3, |

|                 |                      |                      |                      |                      |                                                                       |
|-----------------|----------------------|----------------------|----------------------|----------------------|-----------------------------------------------------------------------|
|                 |                      |                      |                      |                      | Type IV: 3,
Type V: 2                                              |
| PBM-pre  | 20.50 ( $\pm 4.30$ ) | 70.43 ( $\pm 4.90$ ) | 23.07 ( $\pm 0.94$ ) | 11.30 ( $\pm 3.74$ ) | Type I: 2,
Type II: 2,
Type III: 3,
Type IV: 2,
Type V: 1 |
| PBM-post | 21.22 ( $\pm 7.44$ ) | 76.13 ( $\pm 8.03$ ) | 23.48 ( $\pm 1.73$ ) | 11.44 ( $\pm 3.46$ ) | Type I: 3,
Type II: 5,
Type III: 1,
Type IV: 1,
Type V: 0 |

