## Title page

# **Whole-body photobiomodulation for muscle performance enhancement, attenuation of muscular damage and delayed onset muscle soreness in professional soccer athletes – randomized sham-controlled trial**

## Abstract

**Context:** Photobiomodulation (PBM) has recently been applied in sports to enhance physical performance and mitigate muscle damage and delayed-onset muscle soreness (DOMS). These effects may be particularly relevant when PBM is delivered to large body areas through whole-body irradiation. **Objective:** To evaluate the effects of whole-body PBM on muscle damage, DOMS, and muscle performance in professional soccer athletes undergoing a muscle damage induction protocol. **Methods:** A randomized, double-blind, sham-controlled trial was conducted with 30 professional soccer players from a Brazilian team. Participants were randomly allocated into three groups ( $n = 10$  each): (a) PBM-post, (b) PBM-pre, and (c) PBM-sham. Outcomes included serum creatine kinase (CK) levels, DOMS (numeric rating scale [NRS] and pain mapping [mapDOMS]), muscle performance (squat jump [SJ] and countermovement jump [CMJ]), and isometric dynamometry of the knee extensors. All groups received PBM irradiation (active or sham), followed by the muscle damage induction protocol, and subsequent PBM irradiation (active or sham). Assessments were performed at baseline, 24 h, 48 h, and 72 h post-induction. **Results:** CK levels significantly increased ( $p < 0.05$ ) at 24–72 h in the sham group and at 24–48 h in the PBM-post group. In contrast, the PBM-pre group showed no significant increase ( $p > 0.05$ ) across 24–72 h. For DOMS (NRS), the sham group

reported significant increases ( $p < 0.05$ ) from 24–72 h, the PBM-pre group only at 24 h, and the PBM-post group at no time point. DOMS assessed by mapDOMS showed no significant changes ( $p > 0.05$ ) across groups or time points. No significant differences ( $p > 0.05$ ) were observed in muscle performance outcomes among groups. **Conclusion:** Pre-exercise PBM provided protective effects against muscle damage (lower CK) and reduced DOMS at 48–72 h, while post-exercise PBM reduced DOMS consistently at all time points (24–72 h). Neither pre- nor post-exercise PBM improved or worsened muscle performance.

**Keywords:** CK; DOMS; light-emitting diode; low-level laser therapy; recovery

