## Randomization and Allocation Concealment

The randomization was conducted using the website randomization.com, and the participants were allocated into three groups of ten individuals each. To ensure allocation concealment, sealed opaque envelopes were used, containing the randomly assigned interventions: PBM-post, PBM-pre, and PBM-Sham. Only one researcher (therapist 1) was involved in this process, being responsible for applying PBM to all participants. This researcher was blinded to the other assessments in the study, which were conducted by therapist 2. Participants were unaware of which intervention was applied during the study.

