### **b) Measurement of Blood Levels of Creatine Phosphokinase (CK):**

The analyses were carried out by a clinical analysis laboratory (LabCenter Diagnostics Integrates, Itu, SP, Brazil) in a blinded manner, meaning they were unaware of the therapies applied to each participant. Briefly, the athletes rested for about 10 minutes in a seated position before blood collection. The material was labeled, and the forearm was aseptically cleaned with 70% alcohol. Using a 25x8 multiple collection needle, a vein in the antecubital fossa was punctured, and a 5 ml vacuum collection gel tube was inserted for CK analysis. Subsequently, the measurement was performed on a Roche Hitachi 917 biochemical analyzer using enzymatic methodology. A biomedical professional from the laboratory, not involved in the study, assessed the results in U/L. This analysis was conducted at baseline (T1), i.e., before the muscle damage induction protocol, and at 24h, 48h, and 72h after (T3).

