### Creatine Kinase (CK)

The CK data in U/L did not follow a normal distribution, and a logarithmic transformation ( $\log_{10}$ ) was applied. After the transformation, the data showed a normal distribution and homogeneity of variances for conducting parametric tests. Repeated measures ANOVA revealed a moment interaction ( $F_{2,27} < 0.001$ ) and a moment versus treatment interaction ( $F_{2,27} < 0.001$ ). Tukey's post hoc test identified significant differences as shown in the table below:

[figure not shown]
**Table 5.** Mean values ( $\pm$ standard deviation) of creatine phosphokinase (CK) in U/L for the Sham, PBM-pre, and PBM-post groups at pre, 24h, 48h, and 72h after the muscle damage induction protocol:

| Groups   | CK pre                 | CK 24h                  | CK 48h                  | CK 72h                  |
|----------|------------------------|-------------------------|-------------------------|-------------------------|
| Sham     | 289.2 ( $\pm 209.94$ ) | 661.5 ( $\pm 477.24$ )* | 491.6 ( $\pm 285.44$ )* | 523.2 ( $\pm 343.15$ )* |
| PBM-pre  | 249.2 ( $\pm 112.28$ ) | 372.7 ( $\pm 190.58$ )  | 424.2 ( $\pm 248.90$ )  | 392.6 ( $\pm 215.23$ )  |
| PBM-post | 287.8 ( $\pm 199.09$ ) | 794.5 ( $\pm 763.80$ )* | 631.2 ( $\pm 512.08$ )* | 271.44 ( $\pm 133.27$ ) |

**Abbreviations:** PBM (photobiomodulation); CK (creatine phosphokinase). \* p-value  $< 0.05$  in two-way repeated measures ANOVA followed by Tukey's post hoc analysis.

Compared to the pre-moment of the muscle damage induction protocol, there was a significant increase in CK levels in the Sham group ( $p = 0.001$ ) and PBM-post group ( $p = 0.001$ ) at the moment 24h after, while in the PBM-pre group the increase was not significant ( $p = 0.285$ ). When comparing the pre-moment of the muscle damage induction protocol to 48h after, the Sham group had a significant increase in CK ( $p = 0.028$ ), as well as the PBM-post group ( $p = 0.015$ ), while the PBM-pre group did not show a significant increase ( $p = 0.131$ ). In the

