comparison between the pre-moment of the muscle damage induction protocol and 72h after, only the Sham group had a significant increase in CK ( $p = 0.010$ ), while the PBM-pre and PBM-post groups did not show significant increases ( $p = 0.506$ ;  $p = 1.000$ , respectively). In the comparison between groups for the respective CK assessment moments, there were no significant differences ( $p > 0.05$ ). The graphical representation of these results is in Figure 4.

**Figure 4.** Results for creatine phosphokinase (CK) at the evaluated time points (pre-moment of muscle damage induction protocol, 24h, 48h, and 72h after), and experimental groups (Sham, PBM-pre, PBM-post). Values presented in both log10-transformed and raw formats. Data expressed as mean ( $\pm$  standard error).

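### All 30 athletes are said to have completed every procedure, but if CK was recorded in whole U/L the PBM-post 72 h CK mean (271.44) fits nine values and not ten

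*Combined protocol and SAP*

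**What the plan says.** Under Randomization and Allocation Concealment, "the participants were allocated into three groups of ten individuals each". CK is scheduled at baseline, 24 h, 48 h and 72 h. The CK measurement section says that a laboratory professional "assessed the results in U/L" and does not say whether results carry decimals. The SAP summary and Data Analysis make CK the primary endpoint and plan a two-way repeated measures ANOVA, on log10 values if needed. Neither mentions missing values.

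RESULTS then states that all thirty "completed all procedures of this study. Therefore, there were no dropouts, and intention-to-treat analysis was not necessary". Table 5 gives CK means and SDs by group and time without n. Its PBM-post entry at 72 h is 271.44 (SD 133.27). The Abstract reports significant CK rises at 24–72 h "in the sham group and at 24–48 h in the PBM-post group".

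**The concern.** Ten whole numbers have a mean with at most one decimal. Eleven of the 12 means in Table 5 are printed that way, and PBM-post at 72 h is not. That suggests one primary-endpoint value is absent from this mean, although the text says nothing was missed.

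72 h is the only time at which the reported CK pattern differs between PBM-post and Sham. If one value is absent, Table 5 sets ten PBM-post athletes at 48 h against nine at 72 h. A conventional repeated measures ANOVA needs all four values from each athlete, so he was either left out at every time or given a filled-in value. The plan describes neither.

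**Working it through.** **1. The CK cell.** A mean of n whole numbers is T/n with T whole.
- n = 10: 271.44 × 10 = 2714.4, which is not whole. The nearest possible means are 271.4 and 271.5.
- n = 9: 2443/9 = 271.444, printed as 271.44. An SD of 133.27 is attainable with nine whole numbers.
- No other n from 2 to 12 fits, with rounding or truncation.

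**2. Is whole U/L reasonable?** Any one-decimal mean fits ten, so the other 11 means do not prove n = 10. They do bear on the recording unit. With CK recorded to one decimal, ten values would give two-decimal means, and all 11 would have to end in zero by chance (about 1 in 10^11). The exception would be if those 11 were rounded to one decimal and only the twelfth to two. PBM-post at 24 h (794.5) cannot come from nine: 7150/9 = 794.4 and 7151/9 = 794.6.

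**3. Other whole-number variables.**

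| Cell | Mean | Fits |
|---|---|---|
| PBM-post age (Table 4) | 21.22 = 191/9 | 9 only |
| PBM-post years of practice (Table 4) | 11.44 = 103/9 | 9 only |
| Sham and PBM-pre age and years (Table 4) | 18.70, 20.50, 9.60, 11.30 | 10, not 9 |
| PBM-post NRS at 72 h (Table 6) | 2.10 = 21/10 | 10, not 9 |
| Other 11 NRS means (Table 6) | – | 10 |

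The PBM-post phototype counts add to 3 + 5 + 1 + 1 + 0 = 10.

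**4. Chance.** Of 100 two-decimal endings, 90 do not fit ten. Of those 90, 8 fit nine (12 if truncation is also allowed). Three such cells all fitting nine by accident has probability (8/90)³ = 0.07% to (12/90)³ = 0.24%, if the endings are independent.

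**5. The age SD.** Eligibility is 18 to 35 years. Nine whole ages adding to 191 are most spread out as 35, 30 and seven at 18, which gives SD 6.51. Ten ages adding to 212 give at most 6.76. With fractional ages the ceiling is √[(35 − 21.22)(21.22 − 18) × 9/8] = 7.07. The table prints 7.44.

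**6. Size on the mean.** With an absent value X, the ten-athlete mean is (2443 + X)/10. Assume X lay between 100 U/L and the largest single value that the 48 h mean and SD allow, 631.2 + 512.08 × 9/√10 = 2,089 U/L.
- X = 100: 254.3, which is −12% from the baseline mean of 287.8.
- X = 2,089: 453.2, which is +57%.
- As printed: 271.44, which is −6%.

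**7. Size on the 72 h label.** This uses a log-normal approximation, with ln mean = ln(m) − ½ ln(1 + SD²/m²).
- Baseline 5.467 and 72 h 5.496, a ratio of 1.03.
- Adding X = 2,089: (9 × 5.496 + 7.644)/10 = 5.711, a ratio of 1.28.
- Tukey over 12 cells with 81 df has a critical value of 4.76. Matching six printed p-values gives a standard error of 0.102 to 0.136 on the ln scale.
- A difference of 0.244 then has p = 0.87 to 0.98, and X = 100 gives p = 1.00.
- Significance would need a ratio of at least exp(4.76 × 0.102) = 1.62, which means X above about 23,400 U/L.

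**The case against.** The strongest reply is that this rests on an unstated recording unit and could be one mistyped cell. That stands as a limit on confidence. The Table 4 cells are also weaker support than they look. They come from the baseline anamnesis and not from a 72 h blood draw, and nothing links them to the same athlete. The age cell has an impossible SD, so it holds an error or an athlete outside the eligible range. It is also fair that no stated conclusion changes: the Abstract's conclusion credits PBM-post with less soreness and not with lower CK, and no between-group CK difference is claimed.

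A reader might infer more, and the documents do not support it:
- **A dropout.** PBM-post NRS at 72 h fits ten, so at most a laboratory value is absent.
- **A lost high value.** The PBM-post SD falls to 133.27/512.08 = 0.26 of its 48 h size, while Sham rises to 1.20. But if the omitted athlete's 48 h CK was 100, 631, 1,143 or 1,500, the remaining nine have a 48 h SD of 506, 543, 509 or 436. Their ratio is then 0.26, 0.25, 0.26 or 0.31. The same nine athletes show the fall without any lost high value.
- **Proof from the degrees of freedom.** F with 2 and 27 df seems to show that all 30 athletes entered the ANOVA. The same label is printed for every outcome and for both terms. With four times, three groups and 30 athletes, those terms have 3 and 81, and 6 and 81 df. The label says nothing about who was analysed.
- **A hidden complaint.** The sentence "No adverse effects were reported during the study" has no demonstrable link to this cell.

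**Conclusion.** This is a reporting inconsistency on the primary endpoint that needs correction or explanation; confidence is medium. Either 271.44 is a typing error, or one of 120 CK values (one of ten in its cell) is missing or excluded without mention and the completion statement is wrong. The inference assumes whole U/L. The range of about 254 to 453 U/L further assumes a value between 100 and 2,089 U/L. The cause and the handling of the value cannot be read from the documents. So the printed 72 h mean, the size of the PBM-post fall from 48 h, and the set of athletes in the CK ANOVA are all uncertain.

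**What to change.** 1. Check the PBM-post data against source: CK at 72 h, age (mean and SD) and years of practice.
2. Print n per cell in Tables 4 and 5.
3. If 271.44 is an error, correct it. If ten values with decimals exist, list them, and the CK point falls away.
4. Otherwise replace the completion sentence with one saying that one PBM-post CK value at 72 h is missing or excluded, why, and that athletes were analysed as randomised.
5. State how the ANOVA treated this athlete, and print the correct df for each term.
6. If the value is missing, add a linear mixed model of log10 CK on all 119 available values, labelled as a sensitivity analysis.

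The cost is one look at source data, two table edits, a few sentences and at most one re-run on data already held. The mixed-model p-values will differ slightly from the ANOVA, so both should be shown.
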